This study describes the development and validation of the Neuropathic Pain Symptom Inventory (NPSI), a new self-questionnaire specifically designed to evaluate the different symptoms of neuropathic pain. Following a development phase and a pilot study, we generated a list of descriptors reflecting spontaneous ongoing or paroxysmal pain, evoked pain (i.e. mechanical and thermal allodynia/hyperalgesia) and dysesthesia/paresthesia. Each of these items was quantified on a (0-10) numerical scale. The validation procedure was performed in 176 consecutive patients with neuropathic pain of peripheral (n = 120) or central (n = 56) origin, recruited in five pain centers in France and Belgium. It included: (i) assessment of the test-retest reliability of each item, (ii) determination of the factorial structure of the questionnaire and analysis of convergent and divergent validities (i.e. construct validity), and (iii) evaluation of the

ability of the NPSI to detect the effects of treatment (i.e. sensitivity to change). The final version of the NPSI includes 10 descriptors (plus two temporal items) that allow discrimination and quantification of five distinct clinically relevant dimensions of neuropathic pain syndromes and that are sensitive to treatment. The psychometric properties of the NPSI suggest that it might be used to characterize subgroups of neuropathic pain patients and verify whether they respond differentially to various pharmacological agents or other therapeutic interventions.

PMID: 15030944

The full article and the NPSI Assessment tool are contained in **Appendix C** of this clinical study protocol.

SUBJECT DAILY DIARY: Commencing upon administration of the first Erchonia® FX-635™ laser procedure through to completion of the 4-week post-procedure evaluation phase, for a total of 10 consecutive weeks, the subject will be required to complete a Subject Daily Diary at home, recording the following information, as applicable:

- ✓ *Rescue Pain Medication Use:* The subject will record each time a dose of the study rescue pain medication is taken as needed to manage foot pain.
- ✓ *Confirmation of Abstinence from Other Pain Medication Use:* The subject will confirm at the end of each day that he or she refrained from consuming any OTC and/or prescription medication(s) for the indication of pain relief other than the study pain relief rescue medication during that day

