The pre-procedure washout phase comprises the 48-hour (2 day) period immediately preceding the pre-procedure evaluation phase, beginning upon waking on the first 24-hour period.

On each of the two consecutive days of the washout phase, the subject is required to record the specified measures on the washout phase subject record sheets provided by the test site in his or her home and to bring the completed forms to the test site on their pre-procedure evaluation visit.

The investigator will record the dates of the 48-hour washout phase on the subject's take-home record sheets based upon the timeframe required to satisfy the pre-procedure medication abstinence criteria, as applicable.

At the start of the pre-procedure washout phase, the subject commences his or her required abstinence from use of non-study related medications and therapies for the relief of foot pain and simultaneously commences the as-needed consumption of the study rescue medication – OTC Tylenol – for his or her foot pain, that will continue through to the end of the post-procedure evaluation phase.

PRE-PROCEDURE WASHOUT PHASE MEASURES

On each day of the two-day Pre-Procedure Washout Phase, the subject records the following measures on the supplied record sheets, as outlined in the STUDY TEST BATTERY section above.

- Visual Analog Scale (VAS) Foot Pain Rating
- Use of Study Rescue Medication (Tylenol)
- Use of Other Medications

DAY 1: PRE-PROCEDURE EVALUATIONS

The pre-procedure evaluation visit occurs on the day following successful completion of the two-day pre-procedure washout phase and comprises the following activities:

CONFIRMATION OF QUALIFYING VAS RATING

The investigator measures and records the 2 individual VAS foot pain ratings and calculates the average of the 2 VAS foot pain ratings recorded during the 48-hour pre-procedure washout phase. The 2-day average washout phase VAS foot pain rating must be 50 or greater for the subject to proceed with study participation. If the 2-day average washout phase VAS foot pain rating is less than 50, the subject's participation in the study ends at this time.

CONFIRMATION OF STUDY QUALIFICATION

If more than 7 days has passed since initial study qualification evaluation and the pre-procedure evaluation phase, the investigator will confirm with the subject that the information attained during study qualification evaluation has not since changed. If any

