changes are reported, the investigator will review the change(s) to determine if the subject continues to qualify for study participation.

PRE-PROCEDURE VARIABLES

The following pre-procedure variables will be recorded prior to commencement of the procedure administration phase (prior to procedure administration #1), as listed and described in the STUDY TEST BATTERY section above.

- Baseline Foot Variables
- Baseline Concomitant Medication and Therapy Use
- Subject Demographics

PRE-PROCEDURE MEASURES

The following pre-procedure measures will be recorded prior to commencement of the procedure administration phase (prior to procedure administration #1), as listed and described, and according to the methodology outlined, in the STUDY TEST BATTERY section above.

- Visual Analog Scale (VAS) Degree of Pain Rating
- Neuropathic Pain Symptom Inventory (NPSI)

PROCEDURE ADMINISTRATION PHASE

PROCEDURE ADMINISTRATION PROTOCOL

- The procedure administration phase of the study commences within one hour subsequent to recording of the pre-procedure measures and variables, on the same day.
- The procedure administration phase extends over 6 consecutive weeks.
- Each subject receives 12 total procedure administrations with the Erchonia® FX-635™ across the consecutive 6-week procedure administration phase, 2 procedure administrations per week, each procedure administration approximately evenly spaced. That is, each procedure administration will be 3 or 4 days apart with a treatment window of ±1 day.
- Each procedure administration lasts a total of 15 minutes per foot, for a total combined procedure administration time of 30 minutes per session.
- Each procedure administration with the Erchonia® FX-635™ is administered at the investigator's test site.
- The procedure administration protocol for each session is as follows:
 1. The subject enters the procedure administration room and is seated on a chair with the right foot elevated.
 2. The subject is correctly fitted with the laser safety glasses.
 3. The procedure administrator puts on the laser safety glasses and selects the Erchonia® FX-635™ Laser A or B according to the subject's procedure group assignment.
 4. The FX-635™ Laser is positioned around the foot such that each of the 3 laser lights is positioned between 3 and 4 inches away from, but directed toward, a) the top of the foot (dorsal aspect); b) the bottom of the foot (plantar aspect); and c) the posterior tibial nerve within the tarsal tunnel.

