 5. The FX-635™ Laser is activated
 6. The laser diodes laze each of these 3 areas for 15 minutes simultaneously.
 7. The procedures listed in 4. through 6. above is repeated for the left foot.
 8. The investigator and the subject remove the safety glasses.
 9. The subject rises and leaves the procedure administration room.

At each of the procedure administration test site visits, the investigator performs an adverse events evaluation.

PROCEDURE ADMINISTRATION PHASE MEASURES

DAILY MEASURES

Commencing on the same day as the first study procedure administration with the Erchonia® FX-635™ is administered, the subject will begin to record the required information in the Subject Daily Diary, as applicable, at home.

FOLLOWING EACH PROCEDURE ADMINISTRATION

Within 10 minutes following administration of each of the first 11 study procedure administrations with the Erchonia® FX-635™, the subject will record the following at the test site:

- Visual Analog Scale (VAS) Degree of Foot Pain Rating
- Adverse Events Evaluation

POST-PROCEDURE ACTIVITIES

POST-PROCEDURE EVALUATION PHASE

The post-procedure administration evaluation phase of this study will commence immediately following completion of the procedure administration phase and will last 3 months (about 12 weeks).

POST-PROCEDURE EVALUATION VISITS AND MEASURES

There will be 4 post-procedure evaluation visits. The first post-procedure evaluation visit will occur at the test site, and the remaining three post-procedure evaluation visits will take place at the subject's home. The subject will be provided with pre-dated case report forms on which to record the required information on each of those three post-procedure days, and a staff member at the investigator's test site will contact the individual on the designated day to remind him or her to record the required information. These visits, and the associated measures to be recorded at each visit, as listed and described, and according to the methodology outlined, in the STUDY TEST BATTERY section above are as follows:

DAILY MEASURES: AT HOME

The subject will continue to record the required information in the Subject Daily Diary, as applicable, at home, through to the 4 weeks post-procedure evaluation visit.

STUDY ENDPOINT EVALUATION: FOLLOWING COMPLETION OF THE PROCEDURE ADMINISTRATION PHASE: AT THE TEST SITE

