6. K041139; 09/30/04: "The Erchonia EML Laser is indicated as an adjunct to liposuction procedures of the thighs, hips and stomach for reduction of pain associated with the recovery process."

Evaluation Time Point

The study end evaluation time point at which primary study success will be analyzed is at six weeks post-baseline, following completion of the 12th and final study procedure administration with the Erchonia® FX-635™.

Null Hypothesis: There will be no statistically significant difference in the proportion of individual successes, as defined, between the test and control groups.

Alternative Hypothesis: There will be a statistically significant difference in the proportion of individual successes, as defined, between the test and control groups, to the effect of 35% or greater.

SECONDARY EFFICACY OUTCOME MEASURES

Secondary efficacy outcome measures will be evaluated for the following four data sets:

1. The blinded data set only attained from subjects who were initially enrolled in either the test or placebo procedure group and will not include active procedure test data attained from placebo subjects who partook in the post-study open-label procedure administration period after blinding was broken.

For this group, the following secondary efficacy outcome measure will be evaluated:

- a) Change in VAS rating across and between all study evaluation time points within and between treatment groups
 - b) Change in scores on the Neuropathic Pain Symptom Inventory (NPSI) across and between all evaluation points within and between treatment groups
 - c) Differences in the use of rescue pain medication between procedure groups across study duration
2. The combined data set comprising the blinded data set attained from subjects who were initially enrolled in either the test or placebo procedure group, and the active procedure test data attained from placebo subjects who partook in the post-study open-label procedure administration period after blinding was broken, comparing combined test (blinded and non-blinded) to placebo data

For this group, the following secondary efficacy outcome measure will be evaluated:

- a) Change in VAS rating across and between all study evaluation time points to study endpoint evaluation within and between treatment groups
- b) Changes in scores on the Neuropathic Pain Symptom Inventory (NPSI) across and between all evaluation points to study endpoint evaluation within and between treatment groups

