- c) Differences in the use of rescue pain medication between procedure groups across study duration to study endpoint evaluation.
3. The data set comprising the blinded data set attained from subjects who were initially enrolled in the test procedure group, and the active procedure test data attained from placebo subjects who partook in the post-study open-label procedure administration period after blinding was broken, comparing combined blinded to non-blinded test group data

For this group, the following secondary efficacy outcome measure will be evaluated:

- a) Change in VAS rating across and between all study evaluation time points to study endpoint evaluation within and between treatment groups
 - b) Changes in scores on the Neuropathic Pain Symptom Inventory (NPSI) across and between all evaluation points to study endpoint evaluation within and between treatment groups
 - c) Differences in the use of rescue pain medication between procedure groups across study duration to study endpoint evaluation.
4. The data set comprising the blinded data set attained from subjects who were initially enrolled in the placebo procedure group, and the active procedure test data attained from placebo subjects who partook in the post-study open-label procedure administration period after blinding was broken, comparing combined blinded placebo to non-blinded test group data

For this group, the following secondary efficacy outcome measure will be evaluated:

- a) Change in VAS rating across and between all study evaluation time points to study endpoint evaluation within and between treatment groups
- b) Changes in scores on the Neuropathic Pain Symptom Inventory (NPSI) across and between all evaluation points to study endpoint evaluation within and between treatment groups
- c) Differences in the use of rescue pain medication between procedure groups across study duration to study endpoint evaluation.

In addition, the following will be explored:

- ✓ Any deviations in compliance with study required abstinences between procedure groups
 - ✓ Comments provided by subjects
 - ✓ Adverse events
5. The data set comprising the blinded data set attained from subjects who were initially enrolled in the test procedure group, and the active procedure test data attained from placebo subjects who partook in the post-study open-label procedure administration period after blinding was broken, comparing combined blinded to non-blinded test group data

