For this group, the following secondary efficacy outcome measure will be evaluated:

- d) Change in VAS rating across and between all study evaluation time points to study endpoint evaluation within and between treatment groups

- e) Changes in scores on the Neuropathic Pain Symptom Inventory (NPSI) across and between all evaluation points to study endpoint evaluation within and between treatment groups
- f) Differences in the use of rescue pain medication between procedure groups across study duration to study endpoint evaluation.

STATISTICAL METHODS

Efficacy analysis will be according to the intent to treat (ITT) principle by last observation carried forward (LOCF).

Intent to Treat: Subjects will be included in the analysis if they were randomized to study procedure group, had a valid baseline visit including the required Low Back Pain VAS recordings; and received the first study procedure administration.

Last observation carried forward: Missing data will be handled by carrying forward the last observation.

Per-protocol analysis will also be performed for the set of all subjects who were randomized to procedure group and completed the study according to the full protocol.

STATISTICAL ANALYSIS

The primary analysis of efficacy will be through the application of:

- 1) **Fisher's exact test** to compare the proportion of success between the test and the control groups, considering that randomization has been diligently conducted and important covariates between the two groups are well balanced.
- 2) **Parametric ANCOVA model** analysis with the mean change from baseline to study endpoint in foot pain ratings on the VAS as the dependent variable, procedure group as the independent variable of interest and baseline average foot pain VAS rating as a covariate. A two-tailed significance level of 5% will be considered to be statistically significant.

Covariates: The following potential covariate baseline variables will be adjusted, as applicable, through application of an ANCOVA analysis for the continuous variables and linear regression analysis for categorical variables.

- ✓ Baseline VAS rating
- ✓ Baseline NPSI total score
- ✓ Duration of foot pain
- ✓ Time since Diabetes diagnosis
- ✓ Insulin dependent versus non-insulin dependent Diabetes
- ✓ Age
- ✓ Gender

Secondary Measures Analysis

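### No rescue or other analgesic use is scheduled to be recorded after week 10, so the month-3 VAS and NPSI comparisons cannot be checked against it, and the window for the rescue comparison in data set 1 c) is undefined

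*Combined protocol and SAP*

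**What the plan says.** All references are to the combined protocol and SAP.

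- **Planned comparison.** Under Secondary Efficacy Outcome Measures, data set 1 c) is "Differences in the use of rescue pain medication between procedure groups across study duration". The parallel items in data sets 2 to 5 carry a limit that 1 c) lacks: "across study duration to study endpoint evaluation". Items 1 a) and 1 b) compare VAS and NPSI over all evaluation points, which include month 3.
- **Period of rescue use.** The Pre-Procedure Washout Phase section starts abstinence from non-study pain treatments, together with as-needed rescue use "that will continue through to the end of the post-procedure evaluation phase". The Rescue Pain Medication Use section likewise allows rescue for the whole of participation.
- **Length of follow-up.** "The procedure administration phase extends over 6 consecutive weeks", and the Post-Procedure Evaluation Phase section gives a further 3 months, or about 12 weeks.
- **Record of rescue use.** The Subject Daily Diary holds each rescue dose and a daily confirmation of abstinence from other pain medication. It runs from the first procedure "through to completion of the 4-week post-procedure evaluation phase, for a total of 10 consecutive weeks". The post-procedure daily-measures text and the Table of Subject Events give the same stop.
- **Month-3 measures.** The Three Months Post-Procedure Evaluation section and the Table of Subject Events list VAS, NPSI, satisfaction and adverse events. Neither lists medication use.

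**The concern.** The plan permits rescue and requires abstinence for longer than it records either. Two things follow.

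First, the rescue comparison in 1 c) has no stated end. It omits the limit used in the other data sets, and its companions 1 a) and 1 b) reach month 3. The natural reading is therefore that it extends beyond week 6, possibly into weeks with no diary.

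Second, the month-3 VAS and NPSI will be compared between groups with no listed measure of analgesic use at that time. If use differed by group, the pain difference could be masked or enlarged, and the listed data would not show it. The planned exploration of deviations from the required abstinences has the same gap after week 10.

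**Working it through.** **1. The plan's own figure.** Diary length = treatment weeks + post-procedure diary weeks = 6 + 4 = 10 weeks. This matches the stated 10.

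**2. Period in which rescue may be taken after the first procedure.** 6 weeks of procedures + about 12 weeks post-procedure = about 18 weeks.

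**3. Weeks without a scheduled rescue record, by reading of study duration in 1 c).**

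| Reading | Period (weeks) | Without diary | Share |
|---|---|---|---|
| Whole blinded follow-up, 3 months = 12 weeks | 18 | 18 − 10 = 8 | 8/18 = 44.4% |
| Same, 3 months = 13 weeks | 19 | 19 − 10 = 9 | 9/19 = 47.4% |
| Whole follow-up plus the 2-day washout (rescue recorded on separate sheets) | 18 + 2/7 = 18.29 | 8 | 8/18.29 = 43.8% |
| Diary period only | 10 | 0 | 0% |
| To study endpoint, as in data sets 2 to 5 | 6 | 0 | 0% |

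Within the post-procedure phase alone, 8 of 12 weeks (67%) have no diary.

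**4. Which pain assessments fall outside the diary.** Counting from the first procedure, study endpoint is at week 6, the 2-week evaluation at 6 + 2 = week 8, the 4-week evaluation at 6 + 4 = week 10, and the 3-month evaluation at about 6 + 12 = week 18. Only the last lies outside, about 8 weeks after the diary ends.

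**5. How far the rescue-free interval protects the month-3 scores.** The VAS asks about pain at the moment of rating, and subjects are told to hold rescue beforehand. The VAS section of the Study Test Battery gives 4 hours for any pain relief medication. The Rescue Pain Medication Use section and inclusion criterion 13 give 6 hours for the rescue drug. The NPSI recalls the past 24 hours. If it is completed together with the VAS (an assumption), 24 − 6 = 18 or 24 − 4 = 20 of its recall hours lie outside the interval. The interval is also tied to VAS ratings only, and no listed month-3 measure shows whether it was kept.

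**The case against.** The strongest reply is that study duration is undefined, and the protocol specifies a 10-week diary as the rescue record. Item 1 c) can then be read as covering what is collected. That stands: a reader might infer that 44% of the planned data will be missing, but the documents support this only if the term means the whole blinded follow-up.

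A reader might also infer that last observation carried forward will fill weeks 11 to 18 with a week-10 value. The rule reads "Missing data will be handled by carrying forward the last observation". Weeks for which no diary was scheduled are not ordinarily missing data, and nothing in Statistical Methods says that rescue counts will be extended into them. That inference is not supported.

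A third tempting inference is that month-3 pain scores cannot be separated from analgesic use at all. This is too strong for the VAS, since the rescue-free interval addresses recent doses by design. It does not cover the NPSI recall, and compliance at month 3 is not recorded.

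The text also contains broader recording language. The Rescue Pain Medication Use section has doses entered in the diary during the administration and evaluation phase, with no stop date. It also requires departures from baseline medication to be recorded throughout participation. The first statement conflicts with three more specific statements of a week-4 post-procedure stop if it means all 3 months. The second closes a paragraph on non-pain medication and names no form. Both leave wording to reconcile; neither clearly provides a month-3 rescue record.

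Finally, the case report forms in Appendix D are not in the reviewed text, so a medication item on the 3-month form cannot be excluded. The indication sought makes no durability claim, and success is judged at week 6. These points limit the importance of the gap but do not close it.

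**Conclusion.** The point holds as a low-cost improvement. By the protocol's own lists, analgesic use has no clear scheduled record after week 10, while rescue and abstinence run to about week 18. Taken over the whole blinded follow-up, the shortfall for 1 c) is about 8 of 18 weeks (44%; 43.8% to 47.4% depending on how the period is counted). Taken over the diary period, it is zero.

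What remains under either reading is that the month-3 between-group VAS and NPSI comparisons cannot be checked against recorded rescue use. The NPSI is the more exposed of the two.

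The week-6 primary analysis, the 2- and 4-week evaluations and data sets 2 to 5 are not affected. The conclusion assumes that the specific week-4 post-procedure stop governs over the broader recording sentences, and that the unseen 3-month form matches the protocol's list of measures.

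**What to change.** 1. Add to the existing 3-month home form a short item on rescue and other analgesic use over the preceding days, with the time of the last dose. Report it by group beside the month-3 VAS and NPSI.
2. State in data set 1 c) that the rescue comparison covers the 10 diary weeks.
3. Reconcile the recording sentence in Rescue Pain Medication Use with the diary stop given in the Subject Daily Diary section, the post-procedure daily measures and the Table of Subject Events.
4. Reconcile the 4-hour interval in the VAS section with the 6-hour interval in Rescue Pain Medication Use and inclusion criterion 13. Which interval applies is for the sponsor and investigators to settle.

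The cost is one added item on a form already in use and a few sentences of protocol and SAP wording. The item is self-reported recall. It gives a snapshot at month 3, not continuous coverage of weeks 11 to 18.

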The study endpoint evaluation visit will occur at the test site within ten minutes following completion of the procedure administration phase, after administration of the 12th and final procedure administration with the Erchonia® FX-635™.

The following measures will be recorded at this visit:

- Visual Analog Scale (VAS) Degree of Foot Pain Rating
- Neuropathic Pain Symptom Inventory (NPSI)
- Subject Satisfaction With Foot Pain Level
- Subject Perceived Group Allocation and Rationale
- Assessment Investigator Perceived Group Allocation and Rationale
- Adverse Events Evaluation

TWO WEEKS POST-PROCEDURE EVALUATION: AT HOME

Two weeks following completion of the procedure administration phase, the following measures will be recorded:

- Visual Analog Scale (VAS) Degree of Pain Rating
- Adverse Events Evaluation

FOUR WEEKS POST-PROCEDURE EVALUATION: AT HOME

Four weeks following completion of the procedure administration phase, the following measures will be recorded:

- Visual Analog Scale (VAS) Degree of Pain Rating
- Neuropathic Pain Symptom Inventory (NPSI)
- Subject Satisfaction With Foot Pain Level
- Adverse Events Evaluation

THREE MONTHS POST-PROCEDURE EVALUATION: AT HOME

Three months following completion of the procedure administration phase, the following measures will be recorded:

- Visual Analog Scale (VAS) Degree of Pain Rating
- Neuropathic Pain Symptom Inventory (NPSI)
- Subject Satisfaction With Foot Pain Level
- Adverse Events Evaluation

OPEN-LABEL PLACEBO SUBJECT PROCEDURE ADMINISTRATION PERIOD

Following completion of the 3-month post-procedure administration phase, individual subject blinding will be broken. Subjects who had been randomized to the placebo (sham) procedure group will then be offered participation in an additional 6-week post-study open-label procedure administration period during which time they will knowingly receive the active 6-week 12-procedure administration protocol with the Erchonia® FX-635™ Laser as did the subjects initially assigned to the active test procedure group at the time of study enrollment.

Participation in the 6-week post-study open-label procedure administration period is voluntary for subjects who had been assigned to the placebo (sham) procedure group. Participation in the 6-week post-study open-label procedure administration period will not be offered to subjects who had initially been randomized to the active test laser procedure group.

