- The secondary measures that are continuous variables will be analyzed through parametric analysis using ANCOVA. A two-way significance level of 5% will be considered to be statistically significant.
- The secondary measures that are categorical will be evaluated through linear regression analysis.

Satisfaction with Study Outcome Ratings: will be tabulated according to category and reported as percentages. Satisfaction levels will be correlated with subject individual study success and recorded changes in foot pain VAS ratings from Baseline to post-procedure evaluations.

BLINDING EFFICACY EVALUATION

Statistical evaluation of blinding efficacy will be performed as follows:

- (i) The percentage of subjects who correctly perceived their procedure group allocation and the percentage of subjects who did not correctly perceive their procedure group allocation will be calculated.
- (ii) The percentage of times the assessment investigator correctly perceived subjects' procedure group allocation and the percentage of times the assessment investigator did not correctly perceive subjects' procedure group allocation will be calculated.
- (iii) The Fischer's Exact categorical analysis technique for comparison of proportion of successes (accurate procedure group allocation determination) between actual active and placebo subject groups will be performed.

It is anticipated that the results of the Fischer's Exact analysis will not be statistically significant; that is, it is anticipated that both subjects assigned to the active procedure group and subjects assigned to the placebo procedure group will demonstrate a high percentage of accuracy of group allocation determination if the study treatment proves efficacious. Similarly, it is anticipated that assessment investigators will demonstrate a high percentage of accuracy of group allocation determination for both subjects assigned to the active procedure group and subjects assigned to the placebo procedure group, if the study treatment proves efficacious. Therefore, it should be noted that lack of a statistically significant Fischer's Exact analysis result will be considered an indicator of study blinding efficacy, providing additional support to study outcome efficacy, particularly if appropriately supported by the reasoning statements, as explained below.

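### Secondary data set 2 pools former placebo subjects' open-label active records with the test group, so open-label bias is counted as device effect

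*Combined protocol and SAP*

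**What the plan says.** The Secondary Efficacy Outcome Measures section opens with "Secondary efficacy outcome measures will be evaluated for the following four data sets" and then lists five. Each is applied to VAS change, NPSI change and rescue medication use.

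- **Set 1:** the randomised, blinded data only.
- **Set 2:** the blinded data plus active-laser data from placebo subjects who enter the open-label period, "comparing combined test (blinded and non-blinded) to placebo data".
- **Sets 3 and 5** (the same text twice): the blinded test arm and the open-label records, "comparing combined blinded to non-blinded test group data".
- **Set 4:** the placebo arm's blinded data and the open-label records, "comparing combined blinded placebo to non-blinded test group data".

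The Open-Label Placebo Subject Procedure Administration Period section says that blinding is broken for each subject after the three-month follow-up, that "they will knowingly receive the active 6-week 12-procedure administration protocol", and that taking part "is voluntary for subjects who had been assigned to the placebo (sham) procedure group".

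On method, Secondary Measures Analysis says "The secondary measures that are continuous variables will be analyzed through parametric analysis using ANCOVA", at a two-sided 5% level. It names no subject, period or open-label term and no paired analysis. The Primary Efficacy Outcome Measure section excludes open-label data from the primary outcome.

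**The concern.** Randomisation and blinding make a test-versus-placebo difference attributable to the device. Data set 2 gives up both for part of its test group. The added records are unblinded, come only from volunteers, and are collected from about 18 weeks after first treatment (6 weeks of procedures plus about 12 weeks of follow-up). VAS, NPSI and diary-recorded rescue use are all self-reported, so they are open to expectation effects.

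The contrast is still presented as test against placebo and tested at 5%. A significant VAS, NPSI or rescue-use result could therefore be reported from data set 2 when the randomised comparison shows none. The stated purpose of the study is to support a 510(k) submission.

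Two related gaps add to this. Data set 4 compares the placebo subjects with themselves, but no paired method is named. No baseline is named for open-label change either: the ratings listed for that period all follow a procedure. The last earlier ratings are those introduced by "Three months following completion of the procedure administration phase, the following measures will be recorded", which include VAS and NPSI, but the plan does not say they serve as the open-label baseline.

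**Working it through.** **Inputs from the documents.** The plan gives no figure for data set 2. It does give the arm size, which reproduces: 55% versus 20%, two-sided 5%, 80% power, pooled variance without continuity correction gives 29 per group, and 29/(1 − 0.083) = 31.62, rounded to 32. Secondary tests are two-sided at 5%, so 2.5% in each direction.

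**Assumptions (not in the documents).** No true device effect; SD of VAS change 25 mm (20 and 30 also tried); within-subject correlation between placebo-phase and open-label change 0.3, 0.5 and 0.7; m crossovers out of 32; open-label shift s in mm.

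**Step 1: share of the shift credited to the device.** The pooled test group holds 32 unshifted and m shifted records. Its expected difference from placebo is s × m/(32 + m).

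- m = 8: 8/40 = 20%; a 15 mm shift gives 3.0 mm.
- m = 16: 16/48 = 33%; 5.0 mm.
- m = 32: 32/64 = 50%; 7.5 mm.

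**Step 2: effect of the overlap alone.** Take m = 32, correlation 0.5, SD 25.

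- Standard error if all records are treated as independent: √[625 × (1/64 + 1/32)] = 5.41 mm.
- Actual standard error, allowing for the shared subjects: √[625 × (1/64 + 1/32 − 2 × 32 × 0.5/(64 × 32))] = 4.42 mm.

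The test needs about 1.96 × 5.41 = 10.6 mm. With no shift that is 10.6/4.42 = 2.40 true standard errors, a two-sided error of about 1.6% (simulated: 1.8%). Overlap by itself is therefore conservative. The false positives come from the shift.

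**Step 3: false positives favouring the device.** Simulated two-sample t-test of the pooled test group against placebo, 40,000 trials per cell, SD 25. Ranges are over the three correlations; nominal is 2.5%.

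| Open-label shift | m = 8 | m = 16 | m = 32 |
|---|---|---|---|
| 5 mm | not run | 2.6–3.6% | 2.0–4.4% |
| 10 mm | 3.9–4.6% | 5.4–6.8% | 7.8–11.5% |
| 15 mm | 5.5–6.5% | 9.4–11.1% | 19.7–23.8% |
| 20 mm | 7.5–8.4% | 15.9–17.4% | 38.6–40.0% |

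Two-sided error with no shift is 3.4–4.2%, 2.1–3.8% and 0.8–2.8% for m = 8, 16 and 32, against 5% nominal.

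**Step 4: sensitivity.**

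- 15 mm shift, SD 20: 14.1–15.8% (m = 16) and 33.6–35.8% (m = 32). SD 30: 7.1–9.0% and 12.6–17.5%.
- ANCOVA with a baseline covariate (8,000 trials, SD 25), 15 mm: 9.2–11.6% (m = 16) and 20.2–24.2% (m = 32). The planned covariate does not remove the problem.
- A separate simulation in SD units, with a shift of 0.8 SD (20 mm at SD 25) and correlation 0.5, gave 16.6% (m = 16) and 39.1% (m = 32). The first simulation gave 16.4% and 39.1%. The blinded-only comparison stayed near 5% two-sided throughout.

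**Step 5: data set 4.** Here the whole shift enters. A paired test with a 15 mm shift and no true effect is significant in 48–82% of trials at m = 16 and 79–99% at m = 32. Pairing corrects the standard error but not the bias. Run unpaired with no shift at m = 32, the two-sided error falls to 0.1–2.0%.

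**Sets 3 and 5.** No subject is duplicated, but blinded active subjects are compared with self-selected open-label ones, so the groups are not randomised.

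**The case against.** The strongest reply is that the plan contains its own safeguard. The primary outcome excludes open-label data, study success is defined on that outcome alone, and data set 1 reports the same three measures on randomised, blinded data. A favourable data set 2 result would appear beside the proper one. That stands, and it limits the seriousness. But data set 2 is listed as secondary efficacy with a significance level, not among the items the section says will be explored.

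The size is assumed throughout. That also stands. The m = 32 column is an upper bound, since the sample-size section plans for 29 per group remaining. At m = 29 the rates are 7–11%, 18–21% and 34–36% for 10, 15 and 20 mm. A 5 mm shift barely moves the error.

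The direction is not certain either. Blinded-phase entry requires a washout average of at least 50, and no such threshold is stated for open-label entry. If the three-month rating were the baseline, regression to the mean and less room to improve could work against the open-label records. The regression part was put at only about 1–3 mm under similar assumptions. This qualifies the point but does not reverse it.

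Finally, data set 2 could be relabelled exploratory instead of deleted. That would remove the false claim of significance, but the estimate would still mix device effect with open-label bias.

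**Conclusion.** The concern holds. As written, data set 2 is a non-randomised, partly unblinded contrast presented as test against placebo, and a fraction m/(32 + m) of any open-label shift is credited to the device. That fraction is algebra and certain. The false-positive rates are not certain, because they depend on assumed SD, correlation, crossover count and shift. For shifts of 10 to 20 mm at SD 25 they run from about 4% to 40%, against 2.5% nominal. Data set 4 carries the full shift. The repeat of set 3 as set 5 is clerical. The primary outcome, its sample size and data set 1 are not affected, so this should be corrected but does not threaten the main result.

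**What to change.** In the SAP:

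1. Restrict between-group inference on VAS, NPSI and rescue use to data set 1.
2. Delete the combined-test-versus-placebo comparison in data set 2.
3. Analyse data set 4 as paired within-subject change, labelled open-label and uncontrolled.
4. Report sets 3 and 5 once, descriptively, and correct the count of data sets.
5. Name the baseline for open-label change. The three-month VAS and NPSI already collected would serve. They are recorded at home, however, while open-label ratings are taken on site, and no maximum gap before the first open-label procedure is stated. One VAS and NPSI form before that procedure is the sounder choice.

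The cost is SAP wording and less analysis. No new data are needed if the three-month ratings are used; otherwise it is one extra form per crossover subject. The sponsor gives up a pooled comparison that could not be interpreted. The change should be made before analysis, since choosing the baseline or model after unblinding would itself be open to challenge.
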